Official Title:
Tamoxifen to reduce unscheduled bleeding in new users of the
Levonorgestrel-releasing intrauterine system (LNG-IUS)

Principal investigator:
[name] [name]

Professor, Department of Obstetrics and Gynecology
Oregon Health & Science University

Co-investigators:
[name] [name]
[name] [name]
[name] [name]

NCT No.
NCT02824224

Protocol Version Date:
February 12, 2016

Project summary

The 52 mg levonorgestrel-releasing intrauterine system (LNG-IUS, trade name “Mirena” or “Liletta”) is a highly effective method of preventing pregnancy, but its use is often associated with early “nuisance bleeding” which may lead to discontinuation. Given that the LNG-IUS is 20 times more effective at pregnancy prevention than oral contraceptive pills, strategies to increase its acceptability will translate into improved prevention of unplanned pregnancies (1). Many medications have been studied with progestin-only contraceptives such as the LNG-IUS to manage irregular bleeding. The only study to demonstrate a sustained reduction in bleeding lasting for two months was the selective estrogen receptor modulator (SERM) tamoxifen in users of the levonorgestrel (LNG) contraceptive implant (2). The proposed research project will be the first to test the effectiveness of tamoxifen to improve bleeding patterns in users of the LNG-IUS.

This is a randomized, controlled, double blind clinical trial enrolling new users of the LNG-IUS to try to improve frequent or prolonged bleeding after insertion. Participants are randomized to receive tamoxifen 10mg or placebo twice daily for seven days starting 21 days after IUS insertion. All participants will maintain daily bleeding diaries via text or email message and on paper for a total of 51 days, including three weeks of baseline data and 30 days of data following initiation of treatment. The primary anticipated outcome is that women who receive tamoxifen will have a reduction in bleeding/spotting days compared to placebo in the 30 days after starting study drug.

1. DESCRIPTION OF THE PROJECT

1.1 Rationale and objectives of the study

1.1.1 *Rationale*

The 52 mg levonorgestrel-releasing intrauterine system (LNG-IUS) is a highly effective method of reversible contraception with a failure rate within the first year of less than 1% (3). Like other progestin-only methods, the LNG-IUS is associated with bleeding pattern changes ranging from amenorrhea, infrequent and irregular bleeding, to frequent or prolonged bleeding. Bleeding irregularities apart from amenorrhea are most pronounced in the first six months of use. Between 11-26.3% of women experience frequent or prolonged bleeding during LNG-IUS use (4-8). Discontinuation of the LNG-IUS within the first year ranges from 7-30% of users, with the majority of women citing bleeding pattern changes as one of their primary motivations for discontinuation (4-7,9). Patients with excessive bleeding or spotting were 2.7 or 1.8 times more likely to discontinue LNG-IUS, respectively (7). Preventing frequent or prolonged bleeding in LNG-IUS users should decrease discontinuation. Given that long-acting, reversible contraceptives (LARCs) including the LNG-IUS are 20 times more effective at pregnancy prevention than oral contraceptive pills, strategies to increase their acceptability will translate into prevention of unplanned pregnancies (1).

Many prior studies have examined strategies to manage irregular bleeding resulting from progestin-only contraceptives. Mechanisms for irregular bleeding are multifactorial and poorly understood, but may involve changes in vascular growth, vascular fragility, estrogen withdrawal, and disruption in repair mechanisms within the endometrium (10-16). These theories have inspired studies of non-steroidal anti-inflammatory medications, antibiotics, and estradiol preparations to stabilize endometrium and reduce bleeding, but no single approach has shown a consistent benefit (2,15,17,18). The most commonly prescribed medication for persistent bleeding is combined oral contraceptive pills, but these have shown conflicting success in decreasing bleeding, may cause side effects, and are not a therapeutic option for women with contraindications to estrogen (15). Selective progesterone receptor modulators (SPRMs) including mifepristone have shown some promise in reducing bleeding, possibly due to induction of an atrophic endometrium or promotion of tissue repair mechanisms (12,19-21). In humans, single doses of at least 50mg of mifepristone or similar SPRMs consistently reduced either the duration of bleeding episodes, total number of bleeding days, or percentage of bleeding days in users of progestin-only pills (11), depo medroxyprogesterone acetate (DMPA) (22), LNG-IUS (23), and LNG implant (24,25).

Few studies have investigated medications to prevent or treat frequent or prolonged bleeding early in LNG-IUS use. Therapies tested have included selective progesterone receptor modulators, non-steroidal anti-inflammatory drugs, and estrogen patches (16,23,26,27). As mentioned above, mifepristone administered in doses of 100mg monthly starting at LNG-IUS insertion and repeated monthly for three months showed a significant reduction in duration but not frequency of intermenstrual bleeding/spotting in one small, non-randomized, open-label trial (23). Tranexamic acid and mefenamic acid both failed to significantly alleviate breakthrough bleeding in the first 90 days after LNG-IUS insertion when participants were randomized to take them versus placebo when experiencing a bleeding or spotting episode (27). In another randomized controlled prevention trial, Naproxen 500mg twice daily for five days every 4 weeks over 12 weeks after insertion did show a 10% reduction in bleeding/spotting days compared to placebo (RR 0.9, 95% CI 0.84-0.97) whereas estradiol patch use was associated with increased bleeding/spotting days compared to placebo (RR 1.25, 95% CI 1.17-1.34) (26).

In another randomized controlled trial, Warner et al investigated use of a different selective progesterone receptor modulator, CBD-2914, for prevention of unscheduled vaginal bleeding in the first 4 months after LNG-IUS insertion (16). Participants were randomized to

placebo or CBD-2914 50mg for three consecutive days over 4 week intervals administered starting on day 21, day 49, and day 77 after LNG-IUS insertion. Over the first 21 days of use, women reported bleeding/spotting on 70.6% of days (placebo) and 64.7% of days (CBD-2914). In the first 28 days after the first treatment, the percentage of bleeding/spotting days in the treatment arm was an average of 10.6% less than placebo (mean difference of 3 days, $p=0.011$). However, this effect was attenuated after the second treatment, and bleeding/spotting actually increased in the treatment arm compared to the placebo arm after the third treatment (38.2% days with bleeding/spotting vs 28.7%, 6 day increase, $p = 0.022$), suggesting that CBD-2914 offered only an early, short term benefit (16).

One study examined the selective estrogen receptor modulator (SERM) tamoxifen to reduce bleeding days in users of a LNG contraceptive implant who complained of vaginal bleeding irregularities (2). Women were randomized to receive 10mg of tamoxifen or placebo twice daily for 10 days and were followed for 90 days. Women taking tamoxifen had significantly fewer days of bleeding and spotting than placebo over the first two months after dosing (6.24 vs 12.29 days in month one, $p=0.0003$; 6.78 v 11.87 days in month two, $p=0.0008$). The effect waned by the third month. This is the only treatment for progestin-induced bleeding which has shown a sustained bleeding reduction that lasted beyond the treatment period (18). Bleeding stopped within 7 days of starting the medication for 82% of tamoxifen users (compared to 56% of placebo, $p=0.005$). Women reported a higher level of satisfaction with tamoxifen compared to placebo, there were fewer discontinuations due to bleeding over the course of the study (2 vs 9), and side effects were minimal.

Exogenous progestins such as LNG cause decidualization of the endometrium with proliferation of fragile and thin walled vessels, which may be responsible for unscheduled bleeding (13,14). Tamoxifen is a mixed agonist-antagonist to estrogen and competitively inhibits estrogen binding at the estrogen receptor. Whether its effect is agonistic or antagonistic depends on the promoters present in each cell type (28,29). In the endometrium, tamoxifen acts as an antagonist to estrogen receptor beta cells, which may contribute to downregulation of endometrial angiogenesis, leading to decreased breakthrough bleeding (21,28,30). Given the impressive ability of tamoxifen to stop an episode of bleeding and to reduce total bleeding days in users of the LNG implant, it is promising that tamoxifen may have a similar ability to reduce irregular bleeding in users of the LNG-IUS. Developing tamoxifen for this new indication would be a benefit to women and clinicians managing this common contraceptive side effect.

This project will address whether administration of a short course (seven days) of tamoxifen can reduce early bleeding/spotting days in users of the LNG-IUS. Similar to the Warner study, study medication will be administered for 7 days starting 21 days after insertion of LNG-IUS, and bleeding outcomes will be assessed for 30 days after treatment.

1.1.2 Objectives and hypotheses

Hypothesis: Users of the LNG-IUS who receive tamoxifen 21 days after insertion of their device will have a reduction in bleeding/spotting days over the next 30 days compared to placebo.

Primary objective: To determine whether tamoxifen taken preventively in users of the LNG-IUS can reduce the total number of bleeding/spotting days by 40% over 30 days compared to placebo.

Secondary objectives: To determine whether tamoxifen:

1. Leads to a longer duration of bleeding-free days after dosing than placebo
2. Improves satisfaction with the LNG-IUS
 - a. Visual analog scale; anchors 0 = not at all satisfied, 100mm = very satisfied
 - i. With bleeding pattern

- ii. With LNG-IUS overall as a method of contraception
- 3. Improves continuation of the LNG-IUS
 - a. Track discontinuation of the device during the study
- 4. Causes side effects
 - a. Track self-reported adverse events (AEs) and severe adverse events (SAEs)

1.2 Previous similar studies

Tamoxifen has never been studied as an adjunctive therapy to the LNG-IUS. Similar prior studies using other medications were addressed in the rationale section (1.1.1).

1.3 Design and methodology

1.3.1 Research design and general methodological approach

This is a randomized, controlled, double blind clinical trial of 42 women initiating the LNG-IUS. The study will assess the efficacy of oral tamoxifen to decrease bleeding days when taken prophylactically at a dose of 10mg twice daily for seven days starting on day 21 after insertion. The study will be conducted at Oregon Health & Science University (OHSU) in Portland, Oregon. Each subject's involvement will last 51 days and will require a total of up to two study visits in addition to the insertion visit, as well as a daily response to a text or email message about bleeding and use of study medication. Study procedures will be initiated following approval of the protocol by the institutional review board at OHSU. We anticipate that it will take six months to complete enrollment and a total of 15 months to complete all study procedures and analysis.

1.3.2 Number of subjects and statistical power

Our study is powered to detect a clinically significant 40% reduction in bleeding/spotting days over 30 days. No studies to date have examined the effect of tamoxifen on bleeding patterns in LNG-IUS users. The study on CBD-2914 and the LNG-IUS reported mean bleeding/spotting days for 30-day intervals after IUS insertion. Between days 22-51 (analogous to our 30-day follow up period), placebo users had a mean of 18 days of bleeding/spotting with a standard deviation of 7 days (16). Our sample size was calculated to be able to detect a 40% difference in bleeding days (+/- 7 days out of 30) with tamoxifen compared to placebo at 80% power and $\alpha=0.05$ (Aim 1). We propose to enroll 42 women, 21 women in each group (experimental and placebo) to account for a 20% dropout rate (17).

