1.3.3 Criteria for the selection of subjects

Subjects: This study will prospectively enroll English and Spanish speaking women 15-45 years of age seeking initiation of LNG-IUS for contraceptive purposes at the OHSU OB/GYNS clinics. They must have access to a reliable cell phone and must be willing to receive and respond to a daily text or email message to assess bleeding.

Exclusion criteria: Postpartum within six months, pregnant, breast-feeding, LNG-IUS prescribed to treat abnormal uterine bleeding, switching from DMPA, IUS removal and replacement, undiagnosed abnormal uterine bleeding pre-dating placement of IUS, bleeding dyscrasias, anticoagulation use, active cervicitis, allergy to tamoxifen, history of venous thromboembolism, current or past breast or uterine malignancy, use of medication contraindicated with tamoxifen (coumadin, letrozole, bromocriptine, rifampicin, aminoglutethimide, phenobarbital).

Additional exclusions prior to randomization: noncompliance with electronic bleeding diary; clinical evidence of IUD complication (e.g. heavy bleeding suspicious for expulsion (complete or partial); unusual pelvic pain; fever and clinical exam suggesting endometritis.

No vulnerable populations will be specifically recruited or included in this study. Subjects between the ages of 15-18 years of age may be enrolled in this study, but will not be considered a vulnerable population or children since research procedures involve providing birth control information and services.

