Women who enroll in the study will track bleeding and spotting starting on the day after LNG-IUS insertion via response to daily automated text messages. Those who are compliant with text message diaries over the first 14 days (responding 12 or more days, approximately 90% response rate) will be invited by phone to return for study visit 1 (occurring between 14-21 days after IUS insertion). On this scheduling phone call, post-insertion exclusions will be reviewed. Eligible women scheduled for study visit 1 will be randomized by the OHSU research pharmacy on the day prior to their scheduled visit. We anticipate that ensuring compliance with preliminary data collection will help minimize loss to follow up or missing data after randomization. The baseline bleeding data may be used as a covariate in final analysis.

The OHSU research pharmacy will randomize subjects to tamoxifen or placebo through a computer-generated algorithm using a block size of six. Treatment allocation will be double-blinded and study investigators will not have access to the randomization scheme or treatment assignments. The research pharmacy will maintain allocation concealment until completion of the study. Study drug (oral tamoxifen 10mg) will be purchased and routed through the OHSU research pharmacy, and identical placebo will be compounded by the research pharmacy. At

study visit 1, each subject will receive a total of seven days of medication to take home (14 pills). They will be instructed to start this medication on day 21 after insertion of their LNG-IUS.

Women with inadequate responses to the text message diary (less than 12 of 14 days) during the 14-day observation period will be contacted by phone to confirm discontinuation from the study, and they will stop receiving automated text messages.

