1.3.6 Admission procedure

Consistent with usual clinical practice, physical exam including blood pressure check, pelvic examination, urine pregnancy test, cervical cytology evaluation (if not completed within the ASCCP recommended screening interval), and testing for gonorrhea and chlamydia (if indicated based on Centers for Disease Control and Prevention screening algorithms) will be performed at the insertion visit by the primary medical provider. Patients will have access to these results which will be in their primary medical records. Bedside ultrasound may be performed to ensure correct fundal placement of the IUS per provider preference, but this is not routine care and will not be required. Patients will be instructed on how to palpate their IUS strings.

After the medical visit is complete, interested and eligible participants will meet with study staff to complete the informed consent process. Consenting of Spanish-speaking patients will be performed with use of an in-person or phone Spanish interpreter to ensure informed consent. Study forms translated into Spanish will be available. Baseline demographic information will be collected by brief interview, including menstrual history, contraception history, sexual and pregnancy history, BMI/weight, ethnicity, age, and baseline use of panty liners (as advised by Mishell et al to avoid confounding data on bleeding/spotting days) (32). Subjects will receive training on the use of the bleeding diary procedures including the text message/email and paper diaries. Estimated time to complete study procedures during the clinic visit is 20 minutes. For patients who express interest in participating in the study but are unsure of their desire to enroll immediately, there will be the option of returning to the clinic within three days of IUS insertion to complete the enrollment study procedures as described above. Prospective bleeding data will be collected starting on the day of enrollment. Women who enroll after their insertion visit will verbally provide data for bleeding or spotting that occurred after insertion and prior to enrollment.

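### Does the target of 42 enrolled women fall short because enrolment comes before a run-in that removes women before randomisation?

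*Combined protocol and SAP*

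**What the plan says.** Section 1.3.2 gives the target: "We propose to enroll 42 women, 21 women in each group (experimental and placebo) to account for a 20% dropout rate". Section 1.3.1 describes the study in the same terms: "This is a randomized, controlled, double blind clinical trial of 42 women initiating the LNG-IUS".

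The recruitment sections use enrolment for an earlier event. Section 1.3.6 places consent after the insertion visit and gives undecided women "the option of returning to the clinic within three days of IUS insertion to complete the enrollment study procedures". Section 1.3.4 then says: "Women who enroll in the study will track bleeding and spotting starting on the day after LNG-IUS insertion".

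Randomisation comes later, with study visit 1 falling 14 to 21 days after insertion: "Eligible women scheduled for study visit 1 will be randomized by the OHSU research pharmacy on the day prior to their scheduled visit". Between the two events women can be removed. Section 1.3.3 lists "Additional exclusions prior to randomization: noncompliance with electronic bleeding diary" along with clinical signs of an IUD complication. Section 1.3.4 gives the threshold and says how those who miss it are handled: "Women with inadequate responses to the text message diary (less than 12 of 14 days) during the 14-day observation period will be contacted by phone".

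On dropout, Section 1.3.4 expects that "ensuring compliance with preliminary data collection will help minimize loss to follow up or missing data after randomization". Section 1.6 repeats the 20% allowance and discusses it against the 51-day total duration, which includes the run-in.

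**The concern.** If enrolment means consent throughout, 42 enrolled and 21 per group can both be true only when no woman is lost in the run-in, and the protocol plainly expects some to be. The text gives no separate consent target, no expected run-in loss and no replacement rule. The start of the 20% is also open. The comparison with 51 days, and the description of run-in failures as leaving the study, suggest a count from consent. The mention of groups, and the stated purpose of the run-in, suggest a count from randomisation.

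Power is at stake. The target is set close to what 80% power requires. If staff closed recruitment at 42 consents and the full 20% were then lost after randomisation, there would be almost no room for any run-in loss.

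**Working it through.** **Inputs.** Placebo mean 18 days, SD 7 days, difference 7 days (40% of 18 is 7.2), power 80%, alpha 0.05 and 20% dropout come from Section 1.3.2. The two-sided t-test comes from Section 1.3.11.

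**Step 1: reproduce the plan's figure.** The normal approximation is n per arm = 2(1.960 + 0.842)² × SD²/δ². With δ = 7 and SD = 7 this is 2 × 7.85 = 15.7, so 16. The exact noncentral t calculation gives 16.71, so 17. Allowing for dropout, 16/0.8 = 20 and 17/0.8 = 21.25. With δ = 7.2 the exact figure is 15.86, so 16, and 16/0.8 = 20. The stated 21 per arm is consistent with these.

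**Step 2: power at the stated size.** 21 × 0.8 = 16.8 evaluable per arm. Power is 80.2% for 7 days and 82.4% for 7.2 days.

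**Step 3: three readings of the 42.**

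| Reading | Evaluable women | Power (7 / 7.2 days) |
|---|---|---|
| (a) 42 randomised, 20% lost afterwards | 42 × 0.8 = 33.6 | 80.2% / 82.4% |
| (b) 42 consented, 20% covers all loss | 42 × 0.8 = 33.6 | 80.2% / 82.4% |
| (c) 42 consented, run-in loss r, then 20% lost | 42 × (1 − r) × 0.8 | depends on r |

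**Step 4: how much loss 42 consents can absorb.** Total loss that still leaves 80% power:

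- 7 days: 1 − (2 × 16.71)/42 = 20.4%
- 7.2 days: 1 − (2 × 15.86)/42 = 24.5%

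Under reading (c), the run-in loss that can be tolerated is:

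- 7 days: 1 − 0.796/0.8 = 0.5%
- 7.2 days: 1 − 0.755/0.8 = 5.6%

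**Step 5: illustration of reading (c), on assumed rates.** The documents give no run-in loss. Section 1.3.7 says only that earlier response rates exceeded 90%. Suppose daily response is 90%, 93% or 95% and days are independent. Then P(at least 12 of 14) is 84%, 93% or 97%, and 42 consents give about 35, 39 or 41 randomised women. Power (7 / 7.2 days):

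| Loss after randomisation | 90% response | 93% response | 95% response |
|---|---|---|---|
| 20% | 73 / 75% | 77 / 79% | 79 / 81% |
| 10% | 78 / 80% | 82 / 84% | 84 / 86% |
| 5% | 80 / 82% | 84 / 86% | 86 / 88% |

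Six of the 18 values fall below 80%, and five of those six need the full 20% loss after randomisation. The worst is about 7 points short. Missed replies probably cluster within women, so the independence assumption makes these pass rates illustrative only.

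**Step 6: which reading the text supports.** A woman belongs to the tamoxifen or placebo group only once randomised, so 21 per group is a count of randomised women. Section 1.3.1 attaches 42 to the randomised trial. The block size of six in Section 1.3.4 gives 42/6 = 7 complete blocks. All three points favour reading (a).

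**The case for a change.** The strongest case for a change is that the sentence, read with the protocol's own use of the word, sets a consent target. Staff who counted enrolled women would stop at 42, the women lost in the run-in could not be recovered once recruitment closed, and Step 4 shows almost no slack for a 7-day difference. The clarification would also be cheap. At an assumed run-in loss of 5% to 16%, reaching 42 randomised needs about 42/0.95 = 44.2 to 42/0.84 = 50 consents. The 3 to 5 weekly insertions in Section 1.6 amount to 78 to 130 over 26 weeks in one clinic, before eligibility and uptake.

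What stands is that the verb is inconsistent and the start of the 20% is not written down. The predicted harm does not follow. It requires staff to stop at 42 consents although the same sentence calls for 21 in each group, and then enough loss before and after randomisation to pass the limits in Step 4. The run-in is there to reduce loss after randomisation. Section 1.6 reports under 20% loss in similar earlier studies and expects less in this shorter one. The power figures also treat every dropout as contributing nothing, whereas Section 1.3.9 keeps data collected up to withdrawal in the analysis.

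**Conclusion.** The concern does not call for a change. The sample size is arithmetically sound at about 80% power, both under the natural reading (42 randomised, 20% lost afterwards) and under the alternative in which the 20% covers all loss from consent. Power goes below 80% only if recruitment stops at 42 consents and total loss from those women exceeds about 20.4% for a 7-day difference or 24.5% for 7.2 days. Under the assumed response rates above, the shortfall ranges from none to about 7 points, and the largest value needs the least favourable run-in and the full 20% later loss together. Because the documents give no run-in loss rate, no specific shortfall should be attributed to the plan. What remains is a loose use of one word and an unstated starting point for dropout, which a trial team aiming for 21 women per group would resolve sensibly without altering the design, the analysis or the number randomised. These results rest on the plan's SD of 7 days and the two-sided t-test.
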